6.4.3 Planned Analyses

6.4.3.1 Primary Analyses

The primary outcome, MCC₆₀ will be reported using means and standard deviation, with associated 95% confidence intervals at each visit. The mean change of MCC₆₀ between the 2 visits will also be reported with associated 95% confidence intervals. The data will also be plotted in box plots. MCC₆₀ between the 2 visits will be analyzed with a 2-sided paired t-test.

We know from previous studies that skew affect MCC₆₀. Therefore, MCC₆₀ will also be analyzed using a linear repeated measure model including visit number, skew of the deposition histogram as fixed effects. The effect of (visit x skew) as an interaction term will be explored, and if significant, will be included in the model. P-values below 0.05 will be considered significant.

6.4.3.2 Secondary Objectives Analyses

All secondary outcomes, including CC, average clearance over alternative intervals (90 minutes), MCC clearance of central and peripheral lung regions, and pre-bronchodilator FEV₁ will all be reported using means and standard deviations, with associated 95% confidence intervals at each visit. Total CFQ-R, CFRSD-CRISS, and TSQ scores will be considered continuous and will also be reported using means and 95% confidence intervals.

The effect of treatment will be evaluated using 2-sided paired t-tests on all secondary outcomes. A repeated measures model will also be used to analyze MCC₉₀ with visit number and skew as fixed effects. P-values below 0.05 will be considered significant.

Exploration of the effect of site location, age, sex, %FEV₁ and CFQ-R and TSQ scores on MCC₆₀ will be explored using repeated measure models.

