5.2.2 Secondary Outcome Variables

Secondary MCC outcomes will include changes in the rate of cough clearance (CC) from 60-90 minutes, MCC rates measured in other lung compartments (central, peripheral lung) and over other time domains (90 minutes, 6 hours). We will include an analysis of lung function (change in post-bronchodilator FEV₁) as a secondary outcome.

To assess the effect of Bronchitol on respiratory symptoms, we will use the validated respiratory symptom domain of the CFQ-R questionnaire and the CFRSD-CRISS^{11,12}. As treatment burden is also a potential benefit to inhaler delivery of an osmotic agent for airway clearance, the score on the TSQ will be a secondary outcome¹³.

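### Section 6.4.3.2 calls every secondary paired test with P<0.05 significant without a multiplicity rule or exploratory label, and plans no confidence interval for the paired change

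*Combined protocol and SAP*

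**What the plan says.** **Tests.** Section 6.4.3.2: "The effect of treatment will be evaluated using 2-sided paired t-tests on all secondary outcomes". The section then says: "P-values below 0.05 will be considered significant". Neither this section nor 6.4.1 gives a multiplicity adjustment or a testing order, or says that secondary results are exploratory. The plan speaks of exploration only for the visit-by-skew interaction and for variables such as site, age and sex.

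**Outcomes.** Section 6.4.3.2 names four clearance measures ("including CC, average clearance over alternative intervals (90 minutes), MCC clearance of central and peripheral lung regions"), then lung function ("and pre-bronchodilator FEV"₁), then three questionnaire scores. Section 5.2.2 also lists clearance "over other time domains (90 minutes, 6 hours"). The synopsis gives deposition homogeneity indices as a further example of a secondary clearance endpoint. Section 6.4.3.2 adds a repeated measures model for 90-minute clearance with visit and skew as fixed effects.

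**Intervals.** Clearance and FEV₁ outcomes get means and SDs "with associated 95% confidence intervals at each visit". For the questionnaires: "Total CFQ-R, CFRSD-CRISS, and TSQ scores will be considered continuous and will also be reported using means and 95% confidence intervals". That sentence does not say whether the interval is for each visit or for the change. By contrast, 6.4.3.1 plans per-visit intervals for MCC60 and adds that the mean change "between the 2 visits will also be reported with associated 95% confidence intervals".

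**The concern.** Two features of 6.4.3.2 combine. First, every secondary test has its own 5% chance of a false positive, and each one that crosses the line may be called significant. The secondary objectives ask whether Bronchitol leads to improvement in several domains, so a significant secondary result would be read as an answer to that question. The study is open-label, has one arm and expects 22 completers.

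Second, the quantity tested is the within-patient change, but the intervals planned beside it describe the level at each visit. A per-visit interval reflects the spread between patients and does not use the pairing, so it does not show how precisely the change was estimated. In a study of this size, the estimated change and its uncertainty are the most useful secondary result, and the plan does not commit to reporting that uncertainty.

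**Working it through.** **1. The plan's own power figure (6.4.2).** Inputs: n = 22, change 5.4 points, SD of the within-patient difference 8.5 points, two-sided 0.05. The noncentrality is (5.4/8.5) × √22 = 2.98 with 21 degrees of freedom and critical value 2.080. The noncentral t distribution gives power of 81.1%, and 22 is the smallest n that reaches 80%. The stated figure of about 80% reproduces.

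**2. Number of tests.**
- Named in 6.4.3.2: cough clearance, 90-minute, central, peripheral, FEV₁, CFQ-R, CFRSD-CRISS, TSQ = 8.
- With 6-hour clearance from 5.2.2 = 9.
- With deposition homogeneity from the synopsis = at least 10.
- With the second analysis of 90-minute clearance = at least 11 tests.

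**3. Chance of at least one P<0.05 with no true effect.** For k independent tests this is 1 − 0.95^k, and the expected number of false positives is 0.05k. The documents give no correlations between outcomes. The dependent cases therefore use assumed equal pairwise correlations (rho) between the paired changes, with 22 patients and 40,000 simulated trials.

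| Tests | Independent | rho 0.3 | rho 0.5 | rho 0.7 | rho 0.9 | Expected false positives |
|---|---|---|---|---|---|---|
| 8 | 33.7% | 30% | 25% | 20% | 12% | 0.40 |
| 10 | 40.1% | 35% | 29% | 22% | 13% | 0.50 |
| 11 | 43.1% | 38% | 31% | 23% | 13% | 0.55 |

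Every entry is well above 5%, including the row that counts only the eight outcomes named in 6.4.3.2.

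**4. Per-visit interval against change interval.** Let both visits have SD s and let r be the correlation between visits. The per-visit half-width is t × s/√n. The SD of the change is s × √(2(1 − r)), so the half-width for the change is t × s × √(2(1 − r))/√n. The ratio of change to visit is √(2(1 − r)). The documents give no r for any secondary outcome, so the values below are assumptions.

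| r | Change half-width ÷ per-visit half-width |
|---|---|
| 0 | 1.41 |
| 0.5 | 1.00 |
| 0.8 | 0.63 |
| 0.9 | 0.45 |

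The per-visit interval is too narrow as a guide to the change when r is below 0.5 and too wide when r is above 0.5.

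**5. Price of formal adjustment.** Bonferroni over ten tests uses 0.05/10 = 0.005 per test. For an effect as large as the primary one (5.4/8.5 = 0.635 SD), power falls from 81% to about 46%. Over eleven tests (0.0045) it falls to about 44%.

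**The case against.** The strongest reply is that this is a small mechanistic study with one pre-specified, separately powered primary outcome, and that formal multiplicity control of its secondary outcomes is largely a matter of preference. Much of that stands. The primary analysis is untouched, the paired t-test is the right kind of test for these data, and strict adjustment would cost a great deal of power. The reply does not rescue the wording: the plan does not call these results exploratory and does call them significant.

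The count can also be contested. Deposition homogeneity appears only as an example in the synopsis, and deposition skew is a covariate elsewhere in the plan. Without it there are nine outcomes, and ten tests only if the second 90-minute model is counted. This shifts the figures a little and leaves the conclusion as it is.

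A reader might infer that a chance finding is likely. The documents do not support that. For ten tests the risk is 40% at most under the assumptions above, and positive correlation lowers it. Some correlation is expected, because central and peripheral regions lie in the same lung and the 90-minute interval contains the cough period. The risk passes 50% only at 14 independent tests (1 − 0.95^14 = 51.2%). Splitting the TSQ into its four domains would give 13 tests and 48.7%, but 6.4.3.2 speaks of total scores.

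A reader might also infer that the size of the change is hidden. For patients with both values, the difference between the visit means is the mean paired change, and its interval could be worked back from an exact paired P-value. What is missing is a planned interval, not the estimate or the test.

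**Conclusion.** The point holds as a defect in the significance rule and in the planned reporting for secondary outcomes. As written, 6.4.3.2 permits significance claims with a family-wise error of about 13% to 40% over ten tests. The upper figure assumes independence and the range down to 13% assumes pairwise correlations from 0.3 to 0.9. It also sets those claims beside intervals that do not match the paired comparison.

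The documents do not show in which direction the per-visit intervals would mislead, because that depends on the visit-to-visit correlation of each outcome. It would be tempting to use the MCC60 figures (5.4 and 8.5) to argue that a real effect would appear as two overlapping intervals. That does not work: MCC60 is the one outcome for which a change interval is already planned, and no SD of change is given for any secondary outcome.

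One side matter affects which tests are run. FEV₁ is post-bronchodilator in 5.2.2 and pre-bronchodilator in 6.4.3.2, and the CFQ-R is the respiratory domain in the synopsis and 5.2.2 but a total score in 6.4.3.2. These passages should be reconciled; the verdict does not depend on them.

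**What to change.** Make two changes to 6.4.3.2.

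1. Add, in line with what 6.4.3.1 does for MCC60: *The mean paired change between visits will be reported with its 95% confidence interval for every secondary outcome, including the questionnaire scores.*
2. Replace the sentence that calls P-values below 0.05 significant with: *P-values for secondary outcomes are nominal and support no claim on their own.* This should also cover the repeated measures model for 90-minute clearance.

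The cost is one extra table column and the loss of unadjusted secondary significance claims. No new data or patients are needed. Formal adjustment is optional. If the sponsor wants a confirmatory secondary claim, Holm over a fixed list would control the error, but at a cost in power. The Bonferroni figure of about 46% for ten tests shows the scale of that loss, and Holm would recover only part of it.

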6.4.3.3 Safety/Pregnancy-related policy

Adverse events will be collected and coded per MedDRA, version 9 or higher, and tabulated by treatment exposure. The proportion of patients experiencing an adverse event for each treatment exposure will be reported, and 95% confidence intervals will be computed for the proportions using exact binomial methods.

6.4.3.4 Analysis of Subject Characteristics

The following clinico-demographic information from subjects will be collected via chart review and at the screening assessment: Age, gender, race/ethnicity, height, weight, BMI, baseline FEV₁ % predicted, clinical microbiology, CFTR genotype, CF-related comorbidities, and concomitant CF medications. Data will be tabulated and means with standard deviations reported.

6.4.5 Handling of Missing Data

Subjects who do not complete the 2 visits will be listed and reasons for drop-off will be reported. The final dataset will include all subjects who complete both visits per protocol. If any value is missing, it will be considered missing at random and will not be replaced.

7 - Trial Administration

7.1 Ethical Considerations: Informed Consent/Accent and HIPAA Authorization

This protocol will be conducted according to the Declaration of Helsinki, Protection of Human Volunteers (21 CFR 50), Institutional Review Boards (21 CFR 56), and Obligations of Clinical Investigators (21 CFR 312).

Prior to enrolling a subject in the trial, the Investigator must explain the purpose of the study, describe the procedures that will be performed, how the study medication will be used, and explain the potential risks associated with participation in the trial to the subject. Subjects will be informed that their participation is voluntary, and they may withdraw consent to participate at any time. In order to participate in the study, each subject must sign the informed consent (and other locally required documents) after the nature of the study has been fully explained. The consent form must be signed and dated prior to performance of any study-related activity. Subjects must be given the opportunity to ask questions. The subject will be given sufficient time to read the informed consent and to ask additional questions. After this explanation and before entry into the trial, consent should be appropriately recorded by means of either the subject's dated signature or the signature of an independent witness who certifies the subject's consent in writing. After having obtained the consent, a copy of the informed consent form (ICF) must be given to the subject. If the subject is unable to read, an impartial witness must attest the informed consent.

The collection and processing of personal data from subjects enrolled in this trial will be limited to those data that are necessary to investigate the safety, quality, and utility of the investigational agent used in this trial. These data will be processed with adequate precautions to ensure confidentiality. Confidentiality will be maintained throughout the complete data processing.

7.2 Institutional Review Board (IRB) Review

The protocol and consent forms will be reviewed and approved by the IRB on record prior to study initiation. SAEs regardless of relationship to study procedures will be reported to the IRB in accordance with the standard operating procedures and policies of the IRB, and the Investigator will keep the IRB informed as to the progress of the study. The Investigator will obtain assurance of IRB compliance with regulations.

Any documents that the IRB may need to fulfill its responsibilities (such as protocol, protocol amendments, consent forms, information concerning patient recruitment, payment or compensation procedures, or other pertinent information) will be submitted to the IRB. The IRB's written unconditional approval of the study protocol and the informed consent form will be in the possession of the Investigator before the study is initiated. The IRB's unconditional approval statement will be transmitted by the Investigator to the Sponsor or designee prior to

the shipment of study supplies to the site. This approval must refer to the study by exact protocol title and number and should identify the documents reviewed and the date of review.

Protocol and/or informed consent modifications or changes may not be initiated without prior written IRB approval except when necessary to eliminate immediate hazards to the subjects or when the change(s) involves only logistical or administrative aspects of the study. Such modifications will be submitted to the IRB and written verification that the modification was submitted and subsequently approved should be obtained.

The IRB must be informed of revisions to other documents originally submitted for review; serious and/or unexpected adverse experiences occurring during the study in accordance with the standard operating procedures and policies of the IRB; new information that may affect adversely the safety of the patients of the conduct of the study; an annual update and/or request for re-approval; and when the study has been completed.

7.3 Subject Confidentiality

The collection and processing of data from subjects enrolled in this trial will be limited to those data that are necessary to investigate the safety, quality and utility of the investigational agent(s) used in this trial. These data will be processed with adequate precautions to ensure confidentiality. Only a site number and subject number will identify all study subjects on CRFs and other documentation submitted to the Sponsor. Confidentiality will be maintained throughout the complete data processing.

7.4 Deviations/Unanticipated Problems

A protocol violation occurs when the subject, investigator, or the Sponsor fails to adhere to significant protocol requirements affecting the eligibility, subject safety and primary endpoint criteria. Protocol violations for this study include, but are not limited to, the following:

- Failure to meet eligibility criteria
- Defined “major” errors in MCC SOP execution (see Appendix 1)

7.5 Data Collection

The Investigator will prepare and maintain adequate and accurate source documents designed to record all observations and other pertinent data for each subject who signs informed consent.

Study personnel at each site will enter data from source documents corresponding to a subject's visit into the protocol specific CRF when the information corresponding to that visit is available. Scanned paper CRFs will be uploaded along with study images (DICOM format) to the central reading site via a secure Accellion file transfer system. A REDCap database will be designed to house non-image data. Study images will be stored in a secure file location with daily electronic back-up. Subjects will not be identified by name in the study

database or on any study documents to be collected by the Sponsor (or designee) but will be identified by a site number and subject number. Signed consent forms will be saved in a regulatory binder maintained in a locked office at each site.

The Investigator is responsible for all information collected on subjects enrolled in this study. All data collected during the course of this study must be reviewed and verified for completeness and accuracy by the Investigator.

7.6 Data Quality Assurance

After data have been entered into the study database, data validation checks will be applied on a regular basis. Queries will be generated as needed to clarify and confirm submitted data. The study database will be updated in accordance with the resolved queries.

7.7 Study Records

The Investigator must make study data accessible to authorized representatives of the Sponsor (or designee), IRB, and Regulatory Agency (e.g., FDA) inspectors upon request. MCC image data will be maintained electronically. All paper hard copies including ICF, HIPAA authorization, source documents and CRFs will be stored in a regulatory binder at the study site in a locked office. Site PIs must ensure the reliability and availability of source documents from which the information on the CRF was derived.

7.8 Data or Specimen Storage/Security

MCC image data will be transmitted to and maintained by the central reading site via a secure Accellion file transfer system. Visit log sheets and paper CRFs will also be uploaded via the Accellion file transfer system. Key data elements will then be recorded into, a secure, web-based REDCap database. Only study staff will have access to the database.

7.10 Retention of Records

All study documents must be kept secured for a period of two years after database lock.

7.12 Data Safety Monitoring Plan

The Sponsor, [name], is an Assistant Professor of Medicine with experience in clinical research. It will be her responsibility to review any unanticipated problems and adverse events that occur during the conduct of the study.

Adverse events will be collected at study visits by the clinical research coordinator and/or other members of the study team. Each event will be recorded into the study record. The attribution (related, unrelated), severity, and outcome of each event will be reviewed by a site physician investigator. All IRBs of record will be notified of any serious adverse events and any unanticipated, suspected adverse reactions within 48 hours of becoming aware of the event. Other adverse events will be summarized and reported at least annually.

7.13 Study Modification

The primary investigator assumes responsibility for reporting protocol amendments and any necessary ICF revisions to the IRB.

7.14 Study Completion

The expected completion date of the study is March 1, 2023. The primary investigator will notify the IRB of study completion at that time.

7.15 Conflict of Interest Policy

7.17 Funding Source

Pending.

7.18 Publication Plan

The preparation and submittal for publication of manuscripts containing the study results shall be in accordance with a process determined by mutual agreement among the study Sponsor and participating institutions. The publication or presentation of any study results shall comply with all applicable privacy laws, including, but not limited to, the Health Insurance Portability and Accountability Act of 1996.

Appendix 1

Slow Inhalation Large Particle (SILP) Procedure

A. Introduction and Rationale

The SILP MCC Procedure is designed to deliver large (~9 um MMAD) particle aerosol in a controlled delivery at a slow inhalation flow rate (55 ml/sec). This method increases large and small airway deposition while reducing oral and alveolar deposition, and is accomplished without requiring a dosimeter.

B. Equipment and supplies

Pari compressor (Trek-S)

Rotameter (range 0-20 L/min)

Steam sterilizer (Phillips Avent)

Large syringe for leak test (e.g. 1L, 3L spirometry syringe)

Nose clips

SILP Aerosol Delivery Assembly: *(provided by MCC NRC Coordinating Center)*

Mouth piece (disposable)

Pari SPRINT XLent nebulizer (single patient use)

Tubing for connecting nebulizer to compressor

Curved connector (top of nebulizer to exhalation path)

Short straight connector (curved connector to Pall BB50T filter)

Pall BB50T exhalation filter (disposable)

Y-connector (Pall BB50T exhalation filter to exhalation valve and pressure transducer)

Rudolph one way valve to fit in exhalation tubing

Tubing to connect Y-valve to Magnehelic pressure gauge

Magnehelic pressure gauge

Lead shielded case for delivery components

C. Camera quality control procedures:

1. Perform sensitivity test for any camera to be used (once; see below) and is known/documentated
 - a. Take a 10 min image without nearby activity to assess background; record total field of view value (kcps) and save for future reference

- b. Obtain 50 uCi of Tc99m and place in a petri dish in adequate volume to cover bottom of dish
 - c. Place dish containing Tc99m on top of horizontally positioned camera head and record for 1 min. Save kcps value for future reference. This should be at least 6x background value
2. Ensure automatic decay correction is turned off (perform test if unknown/uncertain)
 - a. Open acquisition protocol to be used in MCC study (serial 2 min images; dynamic)
 - b. Place petri dish containing 50 uCi of Tc99m onto camera and record for 60 min
 - c. If decay correction is turned off, a ~10% reduction in kcps should be observed at the end of the imaging period relative to t=0
3. Perform flood image to assess camera homogeneity at least monthly, as per local guidelines.

D. Aerosol delivery setup

- See Figures 1,2,3.
- Before setting up aerosol delivery assembly, inspect the nebulizer jet and use a fine needle to clean the holes if you observe any residual sulfur colloid or foreign material.

[figure not shown]

Figure 1: SILP Aerosol Delivery Assembly Schematic

[figure not shown]

Figure 2: SILP Aerosol Delivery Assembly Setup

Figure 3: Mouthpiece setup

Figure 4: Compressor flow test

E. Testing of equipment

1. Check compressor flow (Fig. 4): Connect the compressor to the rotameter (flow meter), turn on the compressor, the flow should be between 8-10 L/min.
2. Aerosol delivery system leak test (Fig 5): After assembling the aerosol delivery unit, connect a large syringe (e.g. 1L or 3L spirometry calibration syringe) to the aerosol outlet of the Pari SPRINT XLent nebulizer (in place of mouthpiece).
 - a. Gently pull the syringe handle until the needle on Magnehelic pressure gauge deflects toward the left (about $\frac{1}{2}$ way to maximum value);

Figure 5: System Leak Test. In left panel, note leftward deflection of needle on Magnehelic pressure gauge while gentle aspirating with large volume syringe from nebulizer aerosol output.

In right panel, note that the needle stabilizes leftward of zero while obstructing the open port on back of Magnehelic with finger, after releasing suction on syringe.

- b. With syringe in place, use your fingertip to block the bottom/open outlet of the Magnehelic to determine whether there is a leak – the needle deflection should be stable. Release the fingertip quickly then block again check if the needle moves then again remains stable. If the needle keeps moving towards zero after blocking the outlet it means that there is an air leak somewhere in the nebulizer setup, in which case you need to check all the connections, then repeat the test until a satisfactory result is obtained.

3. **Nebulizer airflow test (Fig 6):** With assembled aerosol delivery uni, turn on the compressor and use your hand with clean gloves to block the nebulizer mouth piece outlet. The needle on the Magnehelic pressure gauge should increase 0.2 inches of water (which corresponds to about 55 ml/sec in this setup).

4. **Nebulizer aerosol test:** Put about 0.2ml normal saline in the nebulizer, turn on the compressor, check if the nebulizer generates the aerosol. Once aerosol generation is confirmed, let the compressor run until there is no more aerosol leaving the nebulizer.

Figure 6: Nebulizer airflow test

After testing the nebulizer, securely attach the mouthpiece to the front of the inhalation box for subject use.

F. Placement of Americium-241 sources: Place two Americium-241 sources (1 uCi; shielded side facing patient) along the centerline of the subject's back. The upper marker should be placed over the C7 vertebra; the lower marker should be placed below the inferior lung margin (~13 inches) but within the camera field of view. Use a surgical marker to circle each source, to allow accurate replacement at the 6 hours and/or 24 hours follow-up scan. Tape the Americium sources in place with paper tape. Record the distance between the two Americium markers (log sheet).

G. Transmission scan:

1. Adjust laser pointer to shine on a tape marker placed on subject's neck (near sternal notch) while patient is sitting upright, against camera. Adjust a mirror to allow subject to keep the laser pointer spot on the tape to help maintain alignment later during scanning.
2. Make sure the appropriate camera acquisition protocol is opened (dual isotope state imaging with Co and Am windows). Position the subject in front of camera with the

camera head tilted to 75 degrees. The subject should sit with their back against camera while you place the Co⁵⁷ flat source in front of the subject (~13-15 inches from camera head, resting the Co⁵⁷ source on the chair arms and angling it parallel to camera head (i.e. 75 degrees). Check the image on the computer screen and adjust the camera height to make sure the image is in the right position.

3. Start the scan, noting start time (log sheet) and being aware of approximate Co⁵⁷ exposure time that is expected (see table)
4. Remove the Co⁵⁷ source from camera vicinity once a clear image of the lung outline is seen (record exposure time; log sheet)
5. End the transmission scan acquisition once activity from the Am²⁴¹ sources can be visualized in the appropriate channel. Note time of scan completion (log sheet). Be aware that the total transmission scan time will be longer than the time exposed to Co⁵⁷ in most cases. The Co⁵⁷ exposure time depends on the subject size and activity of the Co⁵⁷ source (see scan time reference table below). Record height and angle of camera head (to be replicated at subsequent studies).

Current Co ⁵⁷ activity	Time for Co ⁵⁷ exposure
15-20 mCi	30 seconds
10-15 mCi	1 minute
7.5 – 10 mCi	90 seconds
5 - 7.5 mCi	2 minutes
2.5 – 5 mCi	2 ½ minutes
< 2.5 mCi (time to get a new source)	3 minutes

H. Background scan:

1. Ensure subject is aligned and laser pointer shines on the tape marker (do not move the tape) while patient is sitting upright against camera. Adjust mirror to allow subject to keep the laser pointer spot on the tape to help maintain alignment during later scanning.
2. With subject appropriately aligned against the camera, begin a 15-minute background scan for use as the current visit background. Ensure that all radioactive sources (except Am²⁴¹ sources on the patient) are removed from the room. Record the average background rate (kcps; read off camera in real time; log sheet).

I. Inhalation Procedure:

1. Subject positioning and preparation: Ensure the proper camera protocol (Tc99 and Am241 windows) is selected. Have the subject wear a disposable gown and gloves. Ask the subject to sit in front of the gamma camera, adjust a bedside table to the proper height to make sure the subject's head is level with the aerosol delivery assembly, without needing to bend neck or slouch once the mouthpiece is in their

mouth. During the maneuvers, they should sit with both feet on ground. Place nose clips on subject once ready to proceed with practice maneuvers.

Practice maneuvers: Before loading any radioaerosol, the inhalation maneuvers should be practiced. After placing nose clips and putting the mouthpiece in their mouth, have the subject briefly hold their breath as you turn on the compressor. If the subject is indeed holding their breath the magnehelic pressure should increase 0.2 in of water (as with nebulizer airflow test – Fig 6). The subject should then immediately begin to gently inhale from the nebulizer for a period of 6 seconds, using a metronome to indicate the inhalation time. The closed inhalation loop limits their inspiratory flow to that provided by the compressor (55 ml/sec). The magnehelic pressure should decrease from the zero setting (leftward; greater than 0.5 inches) in which case the subject is receiving the 55 ml/sec delivered from the nebulizer. At the end of 6 second inhalation the subject should exhale at a constant rate (rightward 0.5 inches of water on Magnehelic) until the compressor has been turned off. *****Make sure the subject does not come off the mouthpiece until instructed by the operator and the compressor has been turned off; otherwise aerosol will be emitted into the room (causing contamination if done during radioaerosol inhalation).***

2. Radioaerosol Inhalation Maneuver: After the subject has demonstrated the proper breathing technique, load the nebulizer with Tc99m-sulfur colloid (3 mCi in 3ml of sterile saline) and begin the inhalation as described above. The subject will come off the mouthpiece (after compressor is turned off, as described above) after each breath of radioaerosol. Following a momentary rest, repeat the next inhalation breath. Generally, 6-10 breaths are required to deposit 40-50 uCi of Tc-SC in the lungs. Use the gamma camera to monitor the deposited isotope dose in kcps with their back pressed against the camera. The target deposited dose of 40-50 uCi should yield camera counts similar to that observed during camera sensitivity test with 50 uCi of Tc isotope, and should be well above the background rate.

After completing the final inhalation, immediately remove the aerosol delivery assembly from room, have the subject drink a small cup of water to flush mouth activity into the stomach, and remove any contaminated materials (gown, glove, etc.). **J. Dynamic scan:**

1. Ensure the subject is lined up properly, using the laser pointer and tape marker on neck. Alignment should be accomplished as soon as possible (ideally within 2-3 min) of completing the aerosol delivery steps.
2. Once aligned, simultaneously start a digital timer and dynamic image acquisition (consecutive 2 minute images; dual windows for Tc^{99m} and Am241). Record the acquisition start time in study log.
3. Ask the patient to refrain from coughing if possible (for first 64 minutes of scan). Record any spontaneous coughs during the dynamic scan period on the data log sheet.
4. Ensure the patient maintains alignment for the first 34 minutes (17 frames); then allow a <6-minute break. Subsequently, it is extremely important that alignment is achieved for the entirety of the first 4 minutes of each ten min period.
5. Terminate data acquisition at the 94 time point.
6. Remove the Am²⁴¹ sources, ensuring their position is adequately marked for placement at later time points (e.g. 3, 6, and 24 hours).

K. Static images at later time points (e.g. 3,6, or 24 hours):

1. Ensure the camera/chair are returned to the prior recorded positions (height and angle).
2. Replace the Am241 sources to their previous locations on the subject.
3. Position the subject in front of the camera using the laser point and mirror.
4. Begin a 15 minute static image acquisition for interval time points \leq 6 hrs after inhalation; use a 30-minute static image acquisition if collecting a later (e.g. 24 hours) time point.
5. Note start/stop time of the image in logsheet. Static images should be performed within 15 min of the nominal timepoint up to 6 hrs; 24-hr images should be within 6 hours of nominal timepoint.

L. Cleaning procedures:

1. After completing the radioaerosol inhalation, leave the nebulizer and connectors in a shielded area (e.g. the lead-shielded delivery box) until the activity has decayed to an acceptable level.
2. When ready to clean, disassemble the delivery apparatus. Discard disposable items (Pall BB50T filter; mouthpiece).
